# LIST OF ABBREVIATIONS

ADT	Androgen depravation therapy
AE	Adverse Event
ALT	Alanine Aminotransferase
ALC	Absolute Lymphocyte Count
AST	Aspartate Aminotransferase
BUN	Blood Urea Nitrogen
BPI	Brief Pain Inventory
CBC	Complete Blood Count
CMP	Comprehensive Metabolic Panel
CR	Complete Response
СТ	Computed Tomography
CTCAE	Common Terminology Criteria for Adverse Events
DLT	Dose Limiting Toxicity
DSMB	Data and Safety Monitoring Board
ECOG	Eastern Cooperative Oncology Group
FACS	Florescence Activated Cell Sorting
H&P	History & Physical Exam
HRQOL	Health-related Quality of Life
HRPP	Human Research Protections Program
IHC	Immunohistochemistry
IV (or iv)	Intravenously
mRCC	Metastatic Renal Cell Cancer
MTD	Maximum Tolerated Dose
NCI	National Cancer Institute
ORR	Overall Response Rate
OS	Overall Survival
PBMCs	Peripheral Blood Mononuclear Cells
PD	Progressive Disease
PFS	Progression Free Survival
p.o.	peros/by mouth/orally
PR	Partial Response
PRN	"Pro re nata" or as needed
QL	Quality of Life
RR	Response Rate
RT	Room Temperature
SABR	Steriotactic Ablative Body Radiation
SAE	Serious Adverse Event
SBRT	Steriotactic Body Radiation Therapy
SD	Stable Disease

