#### 5.1.9 Hematology

CBC with differential.

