# 9.1 Sample Collection Guidelines

Samples will be labeled with the subject's de-identified study number and collection date and delivered for analysis during regular business hours to: NC7: 208; Attn [name]

**9.1.1 Whole blood sample:** Patient's whole blood will be collected in EDTA (Lavender top) tubes for ~ 100 ml at baseline, during RT (one hour after first SABR fraction), post HD IL-2, at 8 week and at 24 week (+/- 2 weeks) and at 1 year starting from the first day of study registration for immunologic assays. In addition, 10 ml will be collected in anti-coagulant-free tubes (Red top) for the collection of sera. The

only exception is the blood collection one hour post first SABR fraction which will be for 20ml in EDTA and 20 ml in anti-coagulant-free tubes The blood will immediately be processed (within 2 hours) by centrifugation (1000g, 15min, 4 °C), collecting the supernatant and freezing at -80 °C in 5 aliquots for future experiments. The pellet will be re-suspended in PBS and PBMC will be isolated using standard protocol. Briefly, the cell suspension will be carefully placed on 10ml polystyrene tube containing 1ml ficoll and centrifuged (400g, 30min, RT). Collect the PBMC region from the ficoll and washed 3x with PBS. Count and freeze cells in 5 aliquots with 10%DMSO 90%FBS in -80°C.

- **9.1.2 Tumor Biopsy Sample:** A CT-guided biopsy of tumor lesion consisting of 4-5 18G needle cores is recommended at the time of registration of the patients to the study. If the patient participated in protocols [such as the Urology Tissue Repository Protocol (STU 032011-187)] or procedures and the tissue confirming kidney cancer diagnosis is in storage and available at UTSW Medical Center or an outside institution, the study team may request a tissue sample. A second biopsy at 8 weeks (+/- 2 week) after the last HD IL-2 treatment is elective.

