- **9.2.4** Chromium Release Cytotoxicity Assays: For cell-mediated cytotoxicity analysis, A 50 μl sample of Cr-labeled target cells (Caki-2 and ACHIN human renal cancer cells) is mixed with 100μl of effector cells (patient PBMC) at various target to effector ratio (E:T ratios). After centrifugation at 100 X G, the cells are incubated for 2 hr at 37°C. The radioactivity of culture supernatant is measured using a gamma counter and percentage of cytotoxicity is calculated. For antibody-dependent cytotoxicity analysis this procedure will be performed with patient's plasma instead of PBMC and the percentage of cytotoxicity is calculated in similar manner. An alternate and non-radioactive labeling method utilizes GAPDH enzyme release from lysed cells called Bioluminescence Non Radioactive Cytotoxicity Assay (aCella-TOX, T Cell Technology, INC) [109, 110].
- **9.2.5** Flow cytometric analysis (FACS): For FACS analysis of cell-surface molecules, the cell samples are stained with fluorescent dye conjugated monoclonal antibodies against the selected markers on ice followed by fixation with 4% paraformaldahyde. Data are acquired on a LSRII (BD Biosciences) and analyzed using FACSDiva software (BD Biosciences). The PBMC of each patient before and after treatment will be analyzed to identify the relative sub-population of CTLs,

regulatory T-Cells, effector memory T cells, MDSCs, neutrophils and NK cells utilizing appropriate cell surface markers (see section 1.5).

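### Blood neutrophils are to be quantified by flow cytometry in frozen Ficoll-separated PBMC, a specimen that cannot give the circulating neutrophil level

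*Combined protocol and SAP*

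**What the plan says.** Three parts of the protocol bear on this.

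- **The assay.** Section 9.2.5 applies flow cytometry to patient PBMC before and after treatment, reporting relative sub-populations. After CTLs, the list continues with "regulatory T-Cells, effector memory T cells, MDSCs, neutrophils and NK cells utilizing appropriate cell surface markers". Section 1.5 announces the same work, and its Table 1, captioned as PBMC subpopulations, has a row for neutrophils.
- **The specimen.** Section 9.1.1 spins the EDTA blood and removes the supernatant. It continues: "The pellet will be re-suspended in PBS and PBMC will be isolated using standard protocol". In detail, "the cell suspension will be carefully placed on 10ml polystyrene tube containing 1ml ficoll and centrifuged"; then "Collect the PBMC region from the ficoll and washed 3x with PBS"; and finally "Count and freeze cells in 5 aliquots with 10%DMSO 90%FBS in -80°C". The List of Abbreviations expands PBMC as "Peripheral Blood Mononuclear Cells".
- **The routine blood count.** Section 5.1.9 specifies "CBC with differential" at screening. Section 5.2.1 requires hematology before each treatment cycle, and the Time and Events Table (5.4) schedules the differential count on treatment and at follow-up. Nothing links these counts to the correlative analysis.

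**The concern.** Neutrophils are polymorphonuclear. On a Ficoll gradient, those of normal density go down with the red cells, and the mononuclear cells stay at the interface. The plan keeps the interface, discards the rest, and then lists neutrophils among the cells to be measured in what was kept.

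Section 1.5 gives the purpose: relative cell levels in tumor and in the peripheral circulation are said to bear on the outcome of an immune response, and are to be used to explore treatment failure. Objective 2.3.1 then looks for immunological correlates or predictors of response. A neutrophil percentage from this specimen could be read as the patient's neutrophil level, and a before-to-after shift as a treatment effect, when the specimen supports neither reading.

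**Working it through.** The protocol gives no figure for this measurement, so there is nothing numerical to reproduce. The check traces the specimen from the draw to the assay, asks what the readout would estimate, and then sees whether the plan already holds a valid source.

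**1. Specimen trace (9.1.1 to 9.2.5).** Whole blood is spun; the cell pellet is resuspended and layered on Ficoll; the PBMC layer is collected, washed three times, counted and frozen in DMSO and serum. No step recovers the granulocyte and red-cell fraction. No whole-blood or lysed-blood flow assay is described for peripheral blood. The red-cell lysis in 9.1.2.2 belongs to the elective 8-week biopsy, and the tissue staining of neutrophils in 9.2.6 is a separate assay. The only blood cells stored for flow cytometry are therefore frozen mononuclear-layer cells.

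**2. What the readout estimates.** For one sample, let N be the circulating normal-density neutrophils, r the small share of them that stays in the layer and survives freezing, L the low-density granulocytes that co-purify, and M the mononuclear cells. Section 9.2.5 states no denominator. Assuming it is all cells in the layer, the measured fraction is

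m = (rN + L) / (rN + L + M).

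When rN + L is small beside M, m ≈ (rN + L) / M. Three things follow.

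- The level of m is not the level of N, because r is unknown and most of N is lost.
- A before-to-after change in m can come from N, r, L or M. The data cannot separate these, since r is not measured.
- If r were zero, m would carry no information on N and would describe L alone, a different biological quantity that the plan does not name.

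**3. Is a valid source already collected?** Section 9.1.1 lists six correlative draws. Against the blood-count schedule in 5.1, 5.2, 5.3 and 5.4:

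- Baseline: a screening count exists, but Section 5.1 allows screening procedures up to 3 months before registration. The count before cycle 1 of IL-2 falls after SABR, so it is not a pre-treatment value.
- One hour after the first SABR fraction: no count scheduled.
- After IL-2 cycle 2: a count at Day 37.
- Week 8: hematology listed at the same visit (5.2.7).
- 24 weeks and 1 year: Section 5.3 lists hematology and correlative blood together at follow-up visits.

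So 6 − 1 = 5 of the draws have a differential count at or near them, subject to visit windows and the age of the screening count. The absolute neutrophil count is already in use, as an eligibility criterion in Section 3.1.9.

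**The case against.** The strongest reply concerns weight. Blood neutrophils are one entry in a list. Section 2.4.4 measures immune response by ELISpot, T-cell proliferation and ELISA. Section 11.3 specifies models only for ELISpot and the proliferation index, and no test or decision rule uses blood neutrophils. All of this stands, and it limits the point to exploratory work.

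It is also fair that the layer is not empty of granulocytes. Low-density or activated neutrophils and granulocytic MDSC can co-purify, and the MDSC row of Table 1 includes myeloid markers. Those cells might even be of interest, but the plan does not say that they are the target.

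A reader might infer four stronger things that the documents do not support:

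- **That the readout can only be noise.** Low-density granulocytes may carry real information, just not about the circulating neutrophil level.
- **That six sampling times are lost.** Section 9.2.5 says only before and after treatment; the six draws serve the whole correlative programme.
- **That the other cell percentages are distorted.** No denominator is stated, and a near-zero neutrophil fraction would barely move one.
- **That the blood assay rests on mouse markers.** Table 1 lists GR-1 and Ly6G, but Section 1.5 commits only to some of the listed markers and Section 9.2.5 to appropriate ones.

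**Conclusion.** The point holds within a narrow scope. Followed as written, the plan yields a PBMC neutrophil percentage that is not valid as a measure of circulating neutrophils, whether as a level or as a change. This affects one cell type in the blood flow panel and any analysis of it under objective 2.3.1. The other listed populations, the tumor-tissue assays, the primary endpoint, the two-stage design, the immune-response endpoints of Section 2.4.4 and safety are unaffected.

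The conclusion rests on two things: the general laboratory fact that Ficoll separation removes most normal-density neutrophils, which agrees with the protocol's own expansion of PBMC, and the absence of any other described blood preparation for flow cytometry. If low-density granulocytes were intended, the defect becomes an unnamed target. The correction is worth making because it is nearly free and replaces an invalid readout with a valid one.

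**What to change.** 1. In Section 9.2.5, remove neutrophils from the PBMC flow list, and mark the neutrophil row of Table 1 as not applying to PBMC. Alternatively, if low-density granulocytes are the target, say so, name human-reactive markers, and do not report the result as a neutrophil level.
2. State that circulating neutrophils are taken as the absolute neutrophil count from the scheduled blood count with differential. For baseline, use the pre-treatment count closest to the baseline correlative draw and record the interval between them. A neutrophil-to-lymphocyte ratio is optional.

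**Cost.** No new blood draw or assay. The change needs a minor amendment with IRB approval (Section 12.7). There would be no neutrophil value one hour after the first SABR fraction, and the baseline count may precede the correlative draw by some weeks.

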Cytokines are hormonal messengers responsible for most of the effects in the immune system such as activation of innate versus adaptive immune response, cellular versus humeral immune response [69, 70]. For example, an increased level of IL-2 and IFN- $\gamma$  suggests activation of Th1 cells leading to activation of macrophages and suggests a cell-mediated adaptive immune response whereas IL-4 and IL-5 may indicate Th2 activation and induction of humoral immunity [28, 70]. An increase in IL-17 may suggest activation of autoimmune responses [71]. Therefore, measurements of serum cytokine levels have generally been used previously in clinical trials as surrogates to assess specific activation of immune pathways [72, 73]. Serum cytokines from this clinical trial before and after SABR will be measured using an extensive array of cytokines to explore the specific immune pathways that are initiated by SABR. The planned array of cytokines will measure levels of the following cytokines before and after treatment for each patients: Th1/Th2/Th17 cytokines: IFN- $\gamma$ , IL-1 $\beta$ , IL-2, IL-4, IL-5, IL-8, IL-10, IL-12p70, IL-13, IL-17 TNF- $\alpha$ ; pro-inflammatory cytokines: GM-CSF, IFN- $\gamma$ , IL-1 $\beta$ , IL-2, IL-6, IL-8, IL-10, IL-12p70, TNF- $\alpha$ ; Chemokines: Eotaxin, MIP-1 $\beta$ , TARC, IP-10, IL-8, MCP-1, MCP-4, KC, and others including IL-6, IL-12, TGF- $\beta$  and HMGB1.

Many surrogate markers for activated and proliferating lymphocytes have been described. Some of these markers include CD25, CD71, CD45RO, CD107a, CD54, CD69, Ki67 and ICOS/CD278 [74-77]. These markers are easily measured with antibodies specific for the markers that are tagged with a fluorophore utilizing FACS analysis. Also using FACS, activation markers on other immune cells such as CD80 and CD 86 on DCs, and inhibitory markers on monocytes such as PD-1 can be measured as surrogates of immune activation or inhibition. These measurements from PBMCs collected from patients before and after treatment will give us further information

regarding the intensity of the immune response. Additionally, PD-L1, the ligand of PD-1, often expressed in tumor cells, can be quantified from patient pre-treatment tumor biopsy.

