## 5.2.6 Day 30-37 (+/- 14 days)

- Physical exam, vital signs
- Hematology
- Serum chemistries
- Second cycle of HD IL-2
- Blood collection for correlative immunologic studies (see section 9.0) on the last day of HD IL-2

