- 9.2.7 Serum Cytokine Analysis: Multiplex cytokine analysis in patient's plasma will be performed in precoated 96 well plates (Human TH1/TH2 10 plex ultrasensitive assay, Meso Scale Discovery - MSD, Maryland, USA) according to manufacturer's instructions. 25 µL of diluent 2 is dispersed into each well. The plate is sealed and incubated by vigorous horizontal shaking for 30 minutes at RT. 25 μL of the patient plasma is added per well and all samples measured in triplicates. Plates are sealed and incubated by vigorous horizontal shaking for two hours at RT. Plates are washed three times with 0.05% Tween 20 in PBS . 25 µL of 1× detection antibody solution is placed per well and sealed plates are incubated by vigorous horizontal shaking for two hours at RT. Plates are washed three times with 0.05% Tween 20 in PBS. 150 µL of 2× Read Buffer T is added to each well. Plates are analysed using the MSD SECTOR Imager 2400 and Discovery Workbench 3.0 software (both from Meso Scale Discovery, USA). The mean value of two wells is taken as the recorded reading, provided that the coefficient of variation (CV) was less than 10%. Concentrations recorded lower than the standard curve are kept as absolute values. For purposes of logarithmic analysis, readings of 0 are adjusted to 0.01 pg/ml. The following cytokines will be measured before and after treatment for each patients: Th1/Th2/Th17 cytokines, IFN-y, IL-1β, IL-2, IL-4, IL-5, IL-8, IL-10, IL-12p70, IL-13, IL-17 TNF-α; proinflammatory cytokines: GM-CSF, IFN-γ, IL-1β, IL-2, IL-6, IL-8, IL-10, IL-12p70, TNF-α; Chemokines: Eotaxin, MIP-1β, TARC, IP-10, IL-8, MCP-1, MCP-4 and others including IL-6, TGF- $\beta$  and HMGB1 (see section 1.5).
- **9.2.8** Western-blot/Immuno-blot: Caki-2 and ACHIN human renal cancer cells lysate will be used to perform immune-blott using plasma collected from patients before and after treatment. The Caki-2 and ACHIN cell 10^6 cells/mL will be lysed in immunoprecipitation assay buffer on ice for 30 min. Standard western blott methodology will be utilized. Briefly, 400 μg of protein will be separated using premade gradient 4% to 12% Bis-Tris gels (Invitrogen, Burlington, ON, Canada) and transferred to nitrocellulose. Patient sera/plasma will be diluted 1/500 in Blotto (5% dry milk powder; 0.1% Tween 20; 50 mmol/L Tris; 150 mmol/L NaCl) and

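### Setting cytokine zeros to 0.01 pg/ml before logs (9.2.7) can create artificial tenfold changes and, depending on the share of zeros, weaken the exploratory cytokine analyses

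*Combined protocol and SAP*

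**What the plan says.** Section 9.2.7 gives the only stated rules for low cytokine values:

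- Sub-curve values: "Concentrations recorded lower than the standard curve are kept as absolute values".
- Zeros: "For purposes of logarithmic analysis, readings of 0 are adjusted to 0.01 pg/ml".
- Replicates: "all samples measured in triplicates", and a few sentences later "The mean value of two wells is taken as the recorded reading", on condition that the CV is below 10%.
- Comparison: "The following cytokines will be measured before and after treatment for each patients". IL-2 is in the list that follows.

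The section gives no detection or quantification limit, no flag for sub-curve values and no sensitivity analysis. Section 11.3 plans GEE for ELISpot and T-cell proliferation and names no cytokine analysis. Section 2.4.4 defines immune response by ELISpot, T-cell proliferation and ELISA. Cytokines therefore serve the pathway exploration in 1.5 and the biomarker objective in 2.3.1.

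On timing, 5.2.6 places one immunologic blood draw in the second HD IL-2 cycle "on the last day of HD IL-2". Section 1.5 says that a raised level of IL-2 and IFN-γ "suggests activation of Th1 cells leading to activation of macrophages and suggests a cell-mediated adaptive immune response".

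**The concern.** An exact zero and a small positive reading below the curve carry nearly the same information: the analyte was not reliably measured. The rule treats them very differently. The positive value keeps its place on the log scale, while the zero goes to a constant chosen without reference to the assay. If one sample of a pair reads zero and the other does not, the log change depends largely on that constant. In a trial of this size, a few such pairs can dominate the mean and SD of an analyte's log change, and any correlation of that change with response.

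The IL-2 analyte raises a separate problem of interpretation. Section 8.1 describes the study drug as a recombinant form of human IL-2. A sample taken while it is being given may contain drug as well as the patient's own cytokine.

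**Working it through.** **Inputs from the documents.** The zero rule, the sub-curve rule and the replicate rule are in 9.2.7. Section 11.2 gives 17 patients at stage 1 and 33 in total (the Study Summary gives a maximum of 38). No cytokine SD, effect size, limit or power is stated, so there is no cytokine figure to reproduce. The one sample-size calculation, for response rate, does reproduce from exact binomial sums: early termination 0.427 (stated 0.43), average size 17 + 16 × (1 − 0.427) = 26.2 (stated 26.2), type I error 0.197 and power 0.805 (design values 0.20 and 0.80). It has no bearing on cytokines beyond fixing the number of patients.

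**Step 1: size of the jump.** A zero paired with a kept reading r differs from it by log10(r / 0.01).

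| r (pg/ml) | log10 difference | fold |
|---|---|---|
| 0.02 | 0.30 | 2 |
| 0.05 | 0.70 | 5 |
| 0.1 | 1.00 | 10 |
| 0.25 | 1.40 | 25 |
| 1 | 2.00 | 100 |

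A tenfold artefact therefore needs a paired reading of at least 0.1 pg/ml.

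**Step 2: effect on the SD and power.** Assume an SD of log10 change of 0.3, a true shift of 0.2 and a two-sided 5% paired t-test. Suppose a share f of pairs has a zero at one visit only, in random direction, giving a jump of ±J. Then SD = √(0.3² + f·J²). For f = 0.10 and J = 1, SD = √(0.09 + 0.10) = 0.44. Power with no such pairs is 0.96 at n = 33 and 0.73 at n = 17. With f = 0.10:

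| J | power, n = 33 | power, n = 17 |
|---|---|---|
| 0.3 | 0.94 | 0.69 |
| 0.7 | 0.85 | 0.55 |
| 1 | 0.72 | 0.43 |
| 2 | 0.36 | 0.20 |

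**Step 3: simulation against half-limit substitution.** All inputs are assumptions: 30 pairs, true 1.5-fold rise, limit 0.5 pg/ml, lognormal levels (SD on the ln scale 0.6 between and 0.3 within patients), additive noise SD 0.15 or 0.25 truncated at zero, one-sided 0.025 paired t-test, 4,000 trials per setting. At medians of 0.3 to 0.5 pg/ml, with about 1.5 to 11% zeros:

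| | 0.01 rule | half-limit |
|---|---|---|
| SD of log10 change | 0.38–0.74 | 0.24–0.31 |
| power | 0.36–0.82 | 0.53–0.92 |
| estimated fold change (true 1.5) | 1.59–1.67 | 1.28–1.47 |

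Half-limit substitution thus gains power here but pulls the fold change toward 1. At median 0.3 it gives 1.28 to 1.31, further from the truth than the 1.64 to 1.65 under the 0.01 rule. A Wilcoxon signed-rank test on the readings as recorded had power 0.59 to 0.97, above both substitution rules.

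**Step 4: where the effect stops.** In the same model, at median 1.0 with low noise, power is 0.97 against 0.99. At median 0.1 the order reverses: 0.21 against 0.06 at 20% zeros, and 0.12 against 0.09 at 29%. A second simulation varied the assumed limit from 0.02 to 1 pg/ml (n = 33, shift 0.2 log10, two-sided 5%). The 0.01 rule against half-limit gave 0.82–0.90 against 0.92–0.93 at 2% zeros, 0.63–0.77 against 0.84–0.85 at 5–6%, and 0.43–0.55 against 0.63–0.65 at 12%. Results at about 22% were mixed, and at 34% the order reversed (0.10–0.13 against 0.03–0.04). With no true change, type I error stayed at 0.04 to 0.06.

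**Step 5: IL-2 timing.** Section 5.2.6 puts one draw on the final HD IL-2 day, 8.1 identifies the drug as recombinant IL-2, 9.2.7 lists IL-2 as an analyte, and 1.5 reads raised IL-2 (with IFN-γ) as Th1 activity. Nothing in the documents shows that the assay separates infused from endogenous IL-2. At that draw, a rise in the IL-2 analyte cannot be attributed to Th1 cells.

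**Step 6: replicates.** Three wells are run and two are averaged. Neither the choice of wells nor the action when the CV is 10% or more is stated. For two zero wells the CV is 0/0, so the acceptance rule is undefined for samples that the 0.01 substitution has to handle.

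**The case against.** The strongest reply is that the size of the effect rests on inputs that the documents do not contain. No limit is given and the assay is described as ultrasensitive. With an assumed limit of 0.02 to 0.05 pg/ml and everything else scaled, the SD under the 0.01 rule falls to 0.31–0.49. This stands: the numbers illustrate the effect and do not predict it for any analyte.

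The CV condition also offers some protection. Wells of 0 and 0.25 have mean 0.125 and SD 0.25/√2 = 0.177, a CV of 141%, and would fail. If the assumed noise is between wells, only about 9–31% of two-well means would pass at these concentrations. This stands in part: the simulated data are not exactly what 9.2.7 would record, but agreeing wells can still differ between visits, and the rule is silent for two zeros.

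Three stronger readings are tempting. A reader might infer that the rule always loses power; Step 4 shows that it does not. A reader might infer false-positive findings; type I error for the mean comparison was not inflated. A reader might infer that every post-treatment IL-2 reading is spurious. In fact 5.4, 9.0 and 9.1.1 also schedule draws after SABR (one hour after the first fraction, before any study IL-2), at 8 weeks, at six months and at one year.

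**Conclusion.** The concern holds in a conditional form. The two rules in 9.2.7 together can turn assay noise into an apparent change of tenfold or more when the paired reading is at least 0.1 pg/ml. With a few to about 12% zeros they can inflate the SD and reduce power in the exploratory fold-change and biomarker work. Analytes well above their limit are barely touched, and with about 20% zeros or more the comparison with half-limit substitution is mixed or reversed. These magnitudes depend on assumed limits, noise, shifts and test.

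The documents do not support any claim against the primary endpoint or the immune-response endpoint in 2.4.4. Nor is a planned cytokine power figure lost, because 11.3 plans no cytokine test. The IL-2 point concerns one analyte at one draw. The replicate point is missing detail and is not evidence that wells would be dropped selectively. This is an inexpensive improvement to an exploratory assay and does not threaten the trial's main conclusion.

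**What to change.** Amend 9.2.7 as follows:

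- State the lower limit of quantification for each analyte and flag every value below it.
- Treat all such values, zeros included, as left-censored in a Tobit or maximum-likelihood model that respects the pairing. Give a rank-based paired test as sensitivity analysis.
- Do not make half-limit substitution the main method, because it biases fold change toward 1.
- State that the IL-2 analyte in the sample from the last day of HD IL-2 is not interpreted as Th1 activation. Other analytes and timepoints are unaffected by this point.
- Reconcile the triplicate and two-well statements: say which wells enter the mean, and what happens when the CV condition fails or all wells read zero.

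The cost is wording only, with no extra patients or samples. The downside is that changes occurring wholly below quantification are no longer counted. The censored model was not simulated here. It also needs a distributional assumption, which is hard to check for an analyte that is mostly below its limit, hence the rank-based companion.
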